10.2. The Number of Participants

We will recruit 1100 - 2000 patients with an interim analysis at 1100 patients.

The sample size is based on the paper:

Pandit JJ. If it hasn't failed, does it work? On 'the worst we can expect' from observational trial results, with reference to airway management devices. *Anaesthesia*. 2012 Jun;67(6):578-83. That explains how binomial confidence intervals can be used in observational airway research of this type.

The conclusions were:

- Investigators in observational studies should state what they regard as 'success' or 'failure' of using the device in question. Where the main endpoint is a continuous variable, researchers should define a justifiable threshold so that it can also be described as a categorical (binomial) endpoint,
- For all results, the upper limit of the 95% confidence interval (CI) should be quoted,
- For airway devices such as SADs, a 95% CI upper limit failure rate $> 2.5\%$ ('the worst we can expect') in the chosen endpoint should generally lead to a conclusion that the device is poor or unsuitable for clinical use, compared with established devices,
- In planning an observational trial, the minimum sample size should be calculated to yield (99% CI) for at least one failure of the device, which generally means that sample sizes should exceed 250,
- Observational studies with < 250 patients are unlikely to provide useful evidence in favour of a device's clinical acceptability, although they may provide useful information suggestive of its lack of acceptability.

We followed all of these conclusions and our expected 1100 recruited patients are a lot more than the 250 expected to show a 2.5% failure rate with 95% CI.

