The LMA® Protector™ is CE marked, produced in a number of sizes, and has been marketed for clinical use since mid-2016, without any design changes until now, and there is as yet only limited trial data on its use beyond pilot studies (14). Given the enhanced design of the LMA® Protector™ there are clear potential advantages to its use, and trial data is required to determine its safety and efficacy. In order to fulfil the ADEPT guidance minimum standard of evidence the device must be further evaluated before it may be safely recommended for purchase by hospital trusts in the UK. We propose a national multi-centre prospective controlled clinical evaluation cohort study, as sufficient to delineate the performance of the device and determine its likely place in clinical practice in the UK (or similar) rather than presupposing we will "recommend it". The LMA® Protector™ is not used in standard care in any of the hospital trusts involved in the study.

Study outline and research questions

We will conduct a prospective multi-centre cohort study to evaluate the performance of the device. The main research questions pertain to the device performance, focusing on quality of the airway, ease of insertion, quality of ventilation, and incidence of complications.

Participants

All patients aged above 18, ASA grade 1 to 3, presenting for elective surgical procedures and requiring and suitable for a supraglottic airway device will be invited to take part in the study. Exclusion criteria are: a) patient refusal, b) below 18 years of age, c) requiring intubation, d) risk factors for aspiration, e) ASA 4 and above, f) mouth opening of less than 2.5cm and deemed to require awake intubation.

Potential risks

The potential risks and burdens are the same compared to using other airway devices during anaesthesia. We will minimise them by ensuring adequate training in the use of the device is used, by recruiting investigators who are anaesthetists with experience of using similar airway devices more than 200 times.

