10.3. Analysis of Outcome Measures

The study will recruit up to 2000 patients, with an interim analysis at 1100 looking at the device failure rate. This is an observational study only. If we apply binomial confidence intervals according to the reference cited, and assume a 'failure rate' of clinical importance as 5%, we find an upper limit 95% CI of 6.54% with 1000 patients. For 2000 patients this upper limit is 6.05%. Thus, the gain of precision in studying up to 2000 patients may be very marginal if this is what an interim analysis at 1100 patients shows. We will however, continue the study if the 'failure rate' is >10% as then the precision in estimate benefit of studying 2000 patients is greater.

The data in this single arm study will be described by descriptive statistics only, using binomial confidence where necessary.

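### No pooled look at the device failure rate is planned before 1100 patients, although section 10.2 accepts that about 250 or fewer can already suggest an unacceptable device

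*Combined protocol and SAP*

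**What the plan says.** **Looks.** Section 10.2: "We will recruit 1100 - 2000 patients with an interim analysis at 1100 patients". Section 10.3 describes the same single look, "with an interim analysis at 1100 looking at the device failure rate". No earlier one is scheduled. The only action tied to it is to continue if the failure rate is above 10%.

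**Criterion.** Section 10.2 lists the conclusions of a methods paper on observational airway studies. One is that an upper 95% limit for failure above 2.5% "should generally lead to a conclusion that the device is poor or unsuitable for clinical use, compared with established devices". Another is that studies of fewer than 250 patients are unlikely to support a device, "although they may provide useful information suggestive of its lack of acceptability". The section then says "We followed all of these conclusions", and compares its size with that number: "our expected 1100 recruited patients are a lot more than the 250 expected to show a 2.5% failure rate with 95% CI". Section 10.3 uses a different figure; there the plan will "assume a 'failure rate' of clinical importance as 5"%.

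**Setting.** Section 3 says the device "is not used in standard care in any of the hospital trusts involved in the study" and that trial data beyond pilot studies are limited.

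**Other oversight.** Section 9.3 requires serious events to be reported within one working day. Section 9.4 requires a yearly progress/safety report, also available on request. Under section 11.2 each of the five sites keeps its own data and sends it to the lead team only when data collection ends.

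**The concern.** The plan accepts that a small sample cannot clear a device but can count against it. It uses the first half of that principle to justify a large study and makes no use of the second half. A device that failed often could be recognised after roughly a quarter of the first 1100 patients, yet nobody is assigned to add up the sites' failures before then. A failed placement that is managed with another device is noted on the CRF and need not be a serious event, so a run of such failures spread over five sites could go unseen as a rate. What is at stake is the exposure of further consenting patients to a device that the accumulated data could already have called into question.

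**Working it through.** **Inputs from the documents.** First look at 1100 (10.2, 10.3); reference size 250 and threshold 2.5% (10.2); failure rate of clinical importance 5%, and the 10% figure (10.3). The true failure rates used below are assumptions, shown as a range.

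**1. Which interval the plan uses.** The exact (Clopper-Pearson) two-sided 95% limits for x failures in n are
- lower = Beta quantile(0.025; x, n − x + 1)
- upper = Beta quantile(0.975; x + 1, n − x)

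50/1000 gives an upper limit of 6.54% and 100/2000 gives 6.05%. Both match section 10.3. One-sided exact limits would be 6.29% and 5.88%, so the plan's interval is two-sided and exact.

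**2. The plan's own criterion at 250 (upper limit above 2.5%).** One failure gives an upper limit of 2.21%; two give 2.86%. So 2 failures in 250 (0.8%) cross it. The chance of crossing is P(X ≥ 2), X ~ Binomial(250, p):
- p = 1%: 71%
- p = 2.5%: 98.7%
- p = 5% or more: above 99.9%

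At 1100 patients, 18 failures are needed, and a device with a true 1% rate crosses only 3% of the time. Used at 250, the upper-limit rule would therefore flag many good devices.

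**3. A stricter rule at 250 (lower limit above 2.5%).** 11/250 has a lower limit of 2.22%. 12/250 has the interval 2.504% to 8.23%. So 12 or more failures (4.8%) are needed. The chance of a flag is P(X ≥ 12), X ~ Binomial(250, p):

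| True failure rate | Chance of a flag |
|---|---|
| 1.5% | 0.05% |
| 2.5% | 2.5% |
| 4% | 30% |
| 5% | 60% |
| 7.5% | 97% |
| 10% | 99.9% |

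**4. Exposure between the two points.** 1100 − 250 = 850 patients. Expected failures: 850 × 0.05 = 42.5, and 850 × 0.10 = 85.

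**The case against.** **A reader might infer that nobody looks before 1100.** The documents do not support that. Section 9.1.4 counts as a serious device effect any event that could have had serious consequences had action not been taken, so some failed airways may be reported within one working day. Each site sees its own failures, and section 11.1 gives the sponsor direct access. The study is planned for 2 years; if recruitment were steady (an assumption), the first yearly report would fall at about 1100/2 = 550 to 2000/2 = 1000 patients. This is real but partial cover, since none of these routes is stated to yield a pooled failure rate.

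**A reader might also infer that the plan's 2.5% criterion would itself expose a bad device at 250.** It would, but it would also flag a device with a true 1% rate 71% of the time. The useful error rates belong to the lower-limit rule, which is proposed here and is not in the plan.

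**The look is weak where the plan sets its own marker.** At the 5% of section 10.3 it flags only 60% of the time. The figure of 85 failures needs a true 10%, which no section predicts. This objection stands.

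**Failure is not defined.** Section 4 has three primary rates and section 7.7 adds failure after three attempts. No single failure count can be returned until one is chosen. This also stands, and it applies equally to the look at 1100.

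**The study is descriptive, the device is CE marked, and operators have used similar devices more than 200 times.** Section 10.2 treats 250 as a minimum sample size and does not commit the plan to a look there. The omission is therefore a design choice and breaks no commitment. Early cases also mix device performance with operator learning.

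**Conclusion.** The concern holds in a limited form. No pooled look at the failure rate is planned before 1100 patients, although section 10.2 accepts that about 250 or fewer can suggest lack of acceptability. An early look on the lower-limit rule would detect clearly high failure rates (97% at 7.5%, 99.9% at 10%) with a 2.5% false-flag chance at exactly 2.5%. It would be unreliable at 4% to 5%. Because it can lead only to a review, and supports no favourable claim, it does not make a favourable conclusion at 1100 or later easier to reach.

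The result assumes independent patients with a common failure rate, one endpoint for which 2.5% is a sensible threshold, and the exact two-sided interval that reproduces section 10.3. The 250 is the number section 10.2 takes from its source; it is not derived here. The sponsor should make this change, but must first name the failure endpoint and settle the data flow.

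**What to change.** **Sections 10.2 and 10.3.**
- Add one review-only look at about 250 patients on one named failure endpoint. One candidate is failure to place the device after three attempts, which section 7.7 already records on the CRF. That section also excludes withdrawn patients' data from the final analysis, so say explicitly that these failures are counted.
- Flag if the exact two-sided 95% lower limit exceeds 2.5% (12 or more of 250). State that this is deliberately stricter than the upper-limit criterion, which 2 of 250 would cross, and print the table of flag probabilities.
- On a flag, the sponsor and chief investigator review the data. They should use the number of previous insertions by the operator, already collected under section 5, to see whether failures cluster in first uses. No favourable claim is made at this look.
- Reconcile the 2.5% in 10.2 with the 5% and the above-10% condition in 10.3.

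**Section 11.2.** Allow each site to return two counts (patients, failures) for this look and for the one at 1100. As written, the section blocks both.

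**Cost.** Two short returns per site, a paragraph in 10.3 and an amendment to 11.2. The downside is a possible flag that reflects operator learning, which is why it prompts a review and not an automatic stop.

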4. OBJECTIVES AND OUTCOME MEASURES

Objectives	Outcome Measures	Timepoint(s) of evaluation of this outcome

		measure (if applicable)
Primary Objective To assess the performance of the LMA Protector	1) First go insertion success rate, 2) First go successful ventilation rate, 3) Percentage of complication free insertions	At time of anaesthesia
Secondary Objectives To assess: 1) Time taken to achieve airway 2) Number of attempts to achieve patent airway 3) Complications during airway insertion 4) Complications during anaesthesia attributed to the airway 5) Complications during device removal 6) Complications after anaesthesia attributed to the airway 7) Quality of ventilation	1) Time to first square capnography waveform 2) Lowest oxygen saturation level 3) Monitor numbers of interventions needed to ensure airway patency 4) Monitor pre-defined complications occurrence during insertion of device, during anaesthesia, and on device removal 5) The quality of ventilation will depend on whether there was: a) adequate chest movement, b) tidal volume $> 7\text{ml/kg}$, c) stable SpO ₂ , and d) square capnography trace	At time of anaesthesia and post-operatively

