7.7. Discontinuation/Withdrawal of Participants from Study

Each participant has the right to withdraw from the study at any time. In addition, the Investigator may discontinue a participant from the study at any time if the Investigator considers it necessary for any reason including:

- Ineligibility (either arising during the study or retrospectively having been overlooked at screening)
- Significant protocol deviation
- Significant non-compliance with treatment regimen or study requirements
- Withdrawal of Consent
- Loss to follow up

The reason for withdrawal will be recorded in the CRF.

If the device cannot be inserted after 3 unsuccessful attempts to insert it, the study will be stopped, an alternative airway device will be used and the failure noted on the CRF. Participants who have been withdrawn will not be replaced. If a patient is withdrawn their research data will not be used in final analysis.

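### Section 10.2 claims every cited conclusion was followed, but no endpoint is designated for the 2.5% benchmark or the >10% rule, and 7.7 leaves three-attempt failures open to exclusion

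*Combined protocol and SAP*

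**What the plan says.** Section 4 gives three primary outcomes of equal rank: "1) First go insertion success rate, 2) First go successful ventilation rate, 3) Percentage of complication free insertions". Each is binary, so each implies a failure rate. Section 8.1 adds tests for adequate ventilation, and Appendix A lists the complications to be noted.

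Section 10.2 summarises the paper on which the sample size rests. The first conclusion is "Investigators in observational studies should state what they regard as 'success' or 'failure' of using the device in question". The third says that a 95% upper limit for the failure rate above 2.5% "in the chosen endpoint should generally lead to a conclusion that the device is poor or unsuitable for clinical use". The section then says "We followed all of these conclusions and our expected 1100 recruited patients are a lot more than the 250 expected to show" (the rate being 2.5%).

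Section 10.3 describes recruitment of up to 2000 patients, "with an interim analysis at 1100 looking at the device failure rate". It goes on to "assume a 'failure rate' of clinical importance as 5%, we find an upper limit 95% CI of 6.54% with 1000 patients", gives 6.05% for 2000 patients, and calls the gain in precision marginal. The continuation rule is "We will however, continue the study if the 'failure rate' is >10" per cent, on the ground that the precision benefit is then greater.

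Section 7.7, on discontinuation and withdrawal, says that after three unsuccessful attempts the study stops for that patient, another device is used and the failure is recorded on the case report form. The same paragraph ends: "If a patient is withdrawn their research data will not be used in final analysis".

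**The concern.** There are two linked gaps.

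The first concerns the claim in 10.2. The benchmark it cites attaches to a chosen endpoint, and the plan chooses none. First-go insertion failure, first-go ventilation failure, any insertion complication and failure after three attempts are all candidates, and they need not agree. Section 10.3 uses a single, undesignated failure rate for the decision on up to 2000 − 1100 = 900 further patients, so the choice could be made after the interim data are seen. It also calls 5% clinically important without relating it to the 2.5% that 10.2 says was followed.

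The second concerns who is counted. If three-attempt failures were treated as withdrawals, the patients in whom the device performed worst would leave both numerator and denominator of the final estimates. For a single-arm study whose result is a set of proportions, that bias runs in one direction only.

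**Working it through.** **Inputs.** From 10.2 and 10.3: interim n = 1100, maximum n = 2000, assumed failure rate 5%, continuation threshold >10%, benchmark 2.5% for the 95% upper limit. From 7.7: three-attempt failure and the rule on withdrawn data. The documents give no expected failure rates, so every failure count below, other than those that follow from the plan's 5%, 10% and 2.5%, is an assumption.

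**1. The plan's own figures.** The exact (Clopper-Pearson) two-sided 95% upper limit for x failures in n is the 0.975 quantile of Beta(x + 1, n − x).

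- 50/1000: 6.54%, as stated in 10.3.
- 100/2000: 6.05%, as stated in 10.3.

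The arithmetic is sound, and the method is identified.

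**2. How 5% relates to 2.5%.**

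| Failures | Observed rate | 95% upper limit |
|---|---|---|
| 55/1100 | 5.00% | 6.46% |
| 100/2000 | 5.00% | 6.05% |
| 17/1100 | 1.55% | 2.46% |
| 18/1100 | 1.64% | 2.57% |
| 36/2000 | 1.80% | 2.48% |
| 37/2000 | 1.85% | 2.54% |

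The benchmark is met only with at most 17 failures in 1100 or 36 in 2000. An observed 5% exceeds it at either sample size.

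**3. What the >10% rule does.** 10% of 1100 is 110, so the rule is triggered at 111 or more failures. The upper limit at an observed 10% is 11.93% for 110/1100 and 11.40% for 200/2000, a gain of 0.53 points. At an observed 5% the gain is 6.46 − 6.05 = 0.41 points.

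**4. Effect of dropping three-attempt failures.** A patient in whom three insertion attempts failed is necessarily a first-go insertion failure. Removing k such patients changes x/n to (x − k)/(n − k), which is smaller whenever x < n. The direction is therefore fixed, and the size depends on assumed counts:

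| First-go failures, all counted | k dropped | Rate after dropping |
|---|---|---|
| 120/1100 = 10.9% | 20 | 100/1080 = 9.3% |
| 121/1100 = 11.0% | 11 | 110/1089 = 10.1% |
| 121/1100 = 11.0% | 22 | 99/1078 = 9.2% |
| 121/1100 = 11.0% | 33 | 88/1067 = 8.2% |
| 55/1100 = 5.0% | 11 | 44/1089 = 4.0% |
| 55/1100 = 5.0% | 22 | 33/1078 = 3.1% |
| 55/1100 = 5.0% | 33 | 22/1067 = 2.1% |

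**5. Could it change the interim decision?** Only if 7.7 is also applied at the interim, which its text does not say. With k = 20 the remaining denominator is 1080, and the rule needs x − 20 > 108, that is x ≥ 129. With all patients counted it needs x ≥ 111. The decision therefore differs only for 111 to 128 first-go failures (10.1% to 11.6% of 1100).

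**The case against.** The strongest reply is that 7.7 already treats three-attempt failure as an outcome. It has its own sentence, which calls the event a failure to be recorded. It is not among the listed reasons for discontinuation, although that list is not closed. Sections 5 and 7.5 record the number of attempts, and Appendix A lists failure to establish an airway as a complication. This is the more natural reading, and it stands. What remains is an ambiguity created by the section heading and by the closing sentence of the same paragraph. A reader might infer that the plan excludes these failures; the documents do not say so. Nor does the exclusion sentence reach the interim, since it speaks only of the final analysis.

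A reader might also infer that the >10% rule cannot be carried out. That is too strong: three binary primary outcomes are named, and each could be compared with 10%. The rule is underspecified, not unusable. Nor do the documents establish that the candidate rates would fall on both sides of 10%, and the precision at stake is about half a percentage point.

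Finally, a reader might take 2.5% as a pass/fail criterion that the study must apply, or 5% as a rival limit. Neither is supported. The analysis is descriptive with no hypothesis test, the cited conclusion is hedged, section 3 disclaims any presumption of recommending the device, and the 5% illustrates precision. Section 10.2 nevertheless says that all the conclusions were followed, and none of these points supplies the endpoint to which the benchmark would apply.

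**Conclusion.** The point holds in limited form. The claim in 10.2 is only partly borne out: the outcomes are binary and imply failures, but no endpoint is designated for the 2.5% benchmark, and the 5% and >10% figures in 10.3 are tied neither to a primary outcome nor to 2.5%. Confidence in this part is high, because it rests on the text and on exact limits that reproduce the plan's own.

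The handling of three-attempt failures is an ambiguity with a likely benign intent, so confidence that it would cause harm is moderate. If the exclusion were applied, the final first-go insertion failure rate would be biased downwards with certainty. In the main example the shift is 10.9 − 9.3 = 1.6 percentage points, which rests on the assumed counts of 20 and 120. An effect on the interim decision needs the further assumption that 7.7 is applied there, and with 20 exclusions it is confined to 111 to 128 first-go failures.

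**What to change.** Before the interim analysis:

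1. In 7.7 and 10.3, state that patients in whom the device fails after three attempts are not withdrawals for the purpose of analysis, and that they count as failures in numerator and denominator at both the interim and the final analysis.
2. In 10.2, either limit or withdraw the statement that all the cited conclusions were followed, or name the endpoint or endpoints to which the 2.5% benchmark applies. State that the 5% and >10% figures concern precision only.
3. In 10.3, designate which primary-outcome failure rate the >10% rule uses. Reporting a rate for each primary outcome is compatible with this, provided one is designated for the interim.

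The cost is a few sentences in 10.2 and 10.3 and one in 7.7, with no added patients or data and no change to how patients are managed. The downside is that the sample-size justification will read less favourably, and the interim rate can no longer be chosen once the data are known.

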10.3. Analysis of Outcome Measures

The study will recruit up to 2000 patients, with an interim analysis at 1100 looking at the device failure rate. This is an observational study only. If we apply binomial confidence intervals according to the reference cited, and assume a 'failure rate' of clinical importance as 5%, we find an upper limit 95% CI of 6.54% with 1000 patients. For 2000 patients this upper limit is 6.05%. Thus, the gain of precision in studying up to 2000 patients may be very marginal if this is what an interim analysis at 1100 patients shows. We will however, continue the study if the 'failure rate' is >10% as then the precision in estimate benefit of studying 2000 patients is greater.

The data in this single arm study will be described by descriptive statistics only, using binomial confidence where necessary.

